8.8.4 Immune-Related Adverse Events

The Immune-related AEs (irAEs) are defined as follows:

Infusion reactions, Hematological, Cardiological, GI, Renal, Pulmonary, Hepatic, Endocrinopathy, Dermatological, Neurological, Ophthalmological, and Rheumatological AEs.

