# 5.6.2 Follow-up for Toxicities

- The emergence of irAEs may be anticipated based on overall experience in clinical studies with similar immunomodulators.
- An irAE is a clinically important AE of unknown etiology associated with the study • drug exposure. IrAEs are typically low grade and self-limited, often occurring after multiple doses, and most frequently involving the GI tract (diarrhea/colitis), skin (rashes), liver (hepatitis), and endocrine systems (a variety of endocrinopathies) and lung (pneumonitis). Serologic, histologic (tumor sample) and immunological assessments should be performed as deemed appropriate by the Investigator, to verify the immune related nature of the AE, and exclude the neoplastic, infectious or metabolic origin of the AE. Management Algorithms (Table 5-5) have been developed to assist Investigators in assessing and managing the following groups of Aes: Infusion reactions, Hematological, Cardiological, GI, Renal, Pulmonary, Hepatic, Endocrinopathy, Dermatological, Neurological, Ophthalmological, and Rheumatological Aes.
- Patients whose treatment is interrupted or permanently discontinued due to an irAE, AE or clinically significant laboratory value, must be followed-up at least once a week (or more frequently if required by institutional practices, or if clinically indicated) for 4 weeks, and subsequently at approximately 4-week intervals, until resolution or stabilization of the event, whichever comes first. Appropriate clinical experts should be consulted as deemed necessary.
- In case of a suspected irAE, the relevant immunological assessments (eg, rheumatoid factor, anti-deoxyribonucleic acid (DNA) Ab, etc.) should be performed and guidelines as outlined in Table 5-5 (and laboratory assessments Section 6.5.6) should be followed.

All patients must be followed up for irAEs, Aes and SAEs for 90 days following the last dose of KY1044 as single agent or in combination with atezolizumab.

Table 5-5 outlines the follow-up evaluation recommended for selected toxicities. For any irAEs/Aes Grade 1 and/or Grade 2, treatment with KY1044 and atezolizumab (if applicable) should be maintained at the determined dose and schedule, unless otherwise specified in Table 5-5.

10-Nov-2021 Version number: 1

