10.7.1 Adverse Events

AEs will be coded using the MedDRA Version 21.0 or higher.

The analysis described in this section will be based on TEAEs and will be tabulated by SOC and/or PT. The number and percentage of patients experiencing each event at least once will be summarized.

A summary of AEs, including the number of events reported, the number of DLTs reported within 21 days of treatment (Phase 1 only), and the number and percentage of

- patients reporting at least one TEAE by SOC and PT,
- patients with at least one CTCAE grade ≥3 TEAE by SOC and PT,
- patients with at least one TEAE by SOC, PT and maximum CTCAE grade
- patients with at least one TEAE by PT,
- patients with at least one TEAE related to KY1044 by PT,
- patients with at least one TEAE related to KY1044 TEAE by SOC and PT,LLOQ
- patients with at least one TEAE related to Atezolizumab by SOC and PT,
- patients with at least one TEAE related to either study drug by SOC and PT,
- patients with at least one greater than or equal to CTCAE grade 3 TEAE related to KY-1044 by SOC and PT,
- patients with at least one greater than or equal to CTCAE grade 3 TEAE related to Atezolizumab by SOC and PT,
- patients with at least one KY1044-related TEAE by SOC, PT and maximum CTCAE grade,
- patients with at least one Atezolizumab-related TEAE by SOC, PT and maximum CTCAE grade,
- patients with an TEAE leading to study discontinuation of either study drug by SOC and PT,
- patients with an TEAE leading to discontinuation of KY1044 by SOC and PT,
- patients with an TEAE leading to discontinuation of Atezolizumab by SOC and PT,
- patients with an TEAE leading to interruption of KY1044 by SOC and PT,
- patients with an TEAE leading to interruption of Atezolizumab by SOC and PT,
- patients with an TEAE leading to interruption of either study drug by SOC and PT,
- patients with an TEAE leading to reduction of KY1044 by SOC and PT,
- patients with at least one TEAE of special interest by SOC and PT
- patients with at least one irAE by SOC and PT

will be presented. In the summary by worst CTCAE grade, the TEAE with the highest or most severe grade will be counted when patients have multiple TEAEs, overall, in a SOC or in a PT as appropriate.

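### SAP 8.8.4 defines immune-related AEs by organ group alone, contradicting protocol 5.6.2 and mislabelling events in the irAE table

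*SAP*

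**What the plan says.** SAP 8.8.4 opens with "The Immune-related AEs (irAEs) are defined as follows" and then gives only a list: "Infusion reactions, Hematological, Cardiological, GI, Renal, Pulmonary, Hepatic, Endocrinopathy, Dermatological, Neurological, Ophthalmological, and Rheumatological AEs". Nothing follows it. The list feeds one row of the AE summaries in SAP 10.7.1, "patients with at least one irAE by SOC and PT". The only restriction on that row is the general one at the head of the section: "The analysis described in this section will be based on TEAEs and will be tabulated by SOC and/or PT".

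Protocol 5.6.2 has its own definition. It begins "An irAE is a clinically important AE of unknown etiology associated with the study" and goes on to name exposure to the drug. It then asks for serological, histological and immunological assessment, as far as the investigator thinks appropriate, to "verify the immune related nature of the AE, and exclude the neoplastic, infectious or metabolic origin of the AE". Only after that does the list of twelve groups appear, and it has another purpose. It names the groups covered by the Table 5-5 algorithms, which exist "to assist Investigators in assessing and managing the following groups of Aes". The title of Table 5-5 confines it to treatment-related toxicities.

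**The concern.** The SAP appears to have taken the scope list of the management algorithms and made it the definition of an irAE, leaving the protocol's definition behind. This is not missing detail. It is a stated rule that gives wrong labels when it is followed.

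Protocol 1.6.3 names promotion of irAEs as a potential risk of KY1044, and 1.6.4 names their aggravation as a potential risk of the combination. A reader of the study report will look at the table labelled irAE to judge that risk. If it mixes immune-mediated events with every GI, blood or respiratory event of any cause, its headline percentage does not describe immune toxicity. It would also differ from what the protocol says an irAE is.

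**Working it through.** No arithmetic applies beyond a count, so the check compares the texts.

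**1. The list.** Infusion reactions (1) plus haematological, cardiological, GI, renal, pulmonary, hepatic, endocrine, dermatological, neurological, ophthalmological and rheumatological (11) make 12 groups. Protocol 5.6.2 gives the same 12 in the same order.

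**2. The two definitions side by side.**

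| Element | Protocol 5.6.2 | SAP 8.8.4 |
|---|---|---|
| Clinical importance | required | absent |
| Association with study drug | required | absent |
| Cause | unknown aetiology, with work-up at the investigator's discretion | absent |
| The twelve groups | scope of the Table 5-5 algorithms | the whole definition |

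**3. Filters elsewhere in the SAP.** Section 8.8.2 defines treatment-emergence, which is a timing rule. Section 8.8.6 defines related AEs, but the irAE row in 10.7.1 does not call on it, whereas other rows name the drug to which the event is related. Section 8.8.5 says AESIs are recorded on the CRF; no such statement is made for irAEs. No mapping from the twelve groups to MedDRA system organ classes or preferred terms is given, so two programmers could build different tables even from the literal rule.

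**4. Three illustrative events, all treatment-emergent.**
- Nausea caused by an opioid falls in the GI group.
- Anaemia from tumour bleeding falls in the haematological group.
- Cough from a respiratory infection falls in the pulmonary group.

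All three are irAEs under SAP 8.8.4. None is an irAE under protocol 5.6.2, because each has a known cause other than study drug.

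**5. Cross-check inside the protocol.** Table 5-4 (dose-limiting toxicities) lists its Grade 3 exceptions for nausea and vomiting, thrombocytopenia, diarrhoea and rash on separate lines from its exception for immune-related AEs. The protocol therefore does not treat membership of an organ group as enough to make an event immune-related.

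**6. What else would show immune toxicity.** SAP 10.7.1 tabulates AESIs, which SAP 8.8.5 takes from protocol Appendix 3. That appendix is the atezolizumab list, and protocol 7.1.6 asks for those AESIs to be reported in atezolizumab-treated patients. For KY1044 itself, 7.1.6 names infusion-related reactions of Grade 3 or above, with overdose and pregnancy for both drugs. In the single-agent arm the irAE row is therefore the main summary dedicated to immune toxicity.

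**The case against.** The other side has several fair points.

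- **The SAP is to be read with the protocol and CRF** (SAP 4.0), so a programmer might fall back on 5.6.2 or on a CRF flag. The CRF is not among the documents, so a flag cannot be ruled out. This softens the claim to what happens if the text is applied literally. It does not remove the defect, because 8.8.4 supplies a competing definition and nothing points away from it.
- **Immune toxicity is visible elsewhere.** For combination patients the AESI table covers most named immune events. TEAEs related to each drug are tabulated by SOC and PT, overall and for Grade 3 or above. The irAE table is itself by SOC and PT, so colitis stays separate from nausea. This stands as partial mitigation. A reader might infer that the trial cannot show immune toxicity at all; these tables show that this goes too far.
- **No endpoint depends on 8.8.4.** A reader might infer that a primary safety endpoint is affected. It is not. The Phase 1 primary endpoints are AEs and SAEs, tolerability and DLTs. DLTs follow protocol Table 5-4, and neither document names irAE incidence as an endpoint.
- **Exclusion of other causes is a work-up instruction** left to the investigator, not a formal clause of the protocol's definition. That is correct. The contradiction rests on clinical importance, unknown aetiology and drug association, which are in the definition.

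**Conclusion.** SAP 8.8.4 is wrong as written. It contradicts protocol 5.6.2 and, taken literally, makes the irAE row in SAP 10.7.1 a count of patients with any TEAE in twelve groups, regardless of cause. The effect is confined to one descriptive table and matters most for single-agent patients.

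Two stronger readings are tempting but unsupported. The first is that the irAE rate would come close to the any-TEAE rate. That needs any-cause AE frequencies by organ group in this population, and the documents give none, so no size can be put on the over-count. The second is that the result would fail to match the atezolizumab monotherapy figures in protocol 1.6.4. Those figures are broad themselves: they include infections (42%), colitis or diarrhoea (20%) and infusion reactions (1.3%), so they are a poor yardstick for a narrow definition.

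The conclusion assumes that the SAP is programmed as worded and that no CRF irAE flag overrides it.

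**What to change.** Replace SAP 8.8.4 with the protocol 5.6.2 definition and make it operational. An irAE would be a TEAE that is assessed as related to KY1044 or atezolizumab under SAP 8.8.6 and whose preferred term is on a list of immune-mediated terms, settled by medical review before database lock. The list should not simply take in every Table 5-5 entry. That table includes anaemia, neutropenia and fatigue, and copying it whole would readmit non-immune cytopenias and fatigue. If the CRF has an investigator irAE flag, use that instead and name it as the data source. Tabulate infusion reactions separately.

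The cost is SAP wording and one term list, using AE terms and relatedness that the 10.7.1 tables already need. The timing allows it: the version 3.0 entry in the SAP's document history has no day filled in, and SAP 4.0 says a final version will be approved before database lock. Version 2.0 already revised the TEAE definition to agree with the protocol.

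The downside is that an immune event judged unrelated, or whose term is not listed, drops out of this table. It still appears in the TEAE tables.

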8.8.5 Adverse Events of Special Interest

Adverse events of special interest (AESI) will be determined during the conduct according to protocol Section 16.3 of the study and will be recorded on CRF.

8.8.6 Related Adverse Events

The related adverse events are defined as those having relationship as "Possibly Related" or "Related".

8.9 Handling of Missing or Partial Dates

Below are rules for imputing missing or partial dates for analyses of medical history, AEs, and concomitant medications. Though imputed for analyses, actual dates (missing or partial) will be reflected in listings. Otherwise, there will be no imputation of missing data values. Data on patients who withdraw early will be summarized up until the time of withdrawal.

Missing or partial dates for medical history will be imputed as follows:

- If only the day is missing, it will be imputed with the 1st day of the month.
- If both the day and month are missing, the month and day will be imputed with January 1st.
- If the date is completely missing, no imputation will be performed.

Missing or partial dates for AEs and concomitant medications will be imputed as follows:

- Start Date
 - If only the day is missing and the month and year are the same as the month and year of the first dose date, then the day will be imputed with the day of the first dose date. Otherwise the day will be imputed with the first day of the event month.
 - If both the day and month are missing and the year is the same as the year of the first dose date then they will be imputed with the month and day of the first dose date. Otherwise they will be imputed with the January 1st.
 - o If the start date is completely missing, the date will be imputed with the first dose date.
 - If the stop date is complete and the imputed start date is after the stop date, then the imputed start date will be set to the stop date.
- Stop Date

- If only the day is missing and the month and year are the same as the month and year of the study discontinuation date, then the day will be imputed with the day of the study discontinuation date. Otherwise the day will be imputed with the last day of the event month.
- If both the day and month are missing and the year is the same as the year of the study discontinuation then they will be imputed with the month and day of the study discontinuation date. Otherwise they will be imputed with the December 31st.
- If the stop date is completely missing, then it will be imputed with the study discontinuation date.

Note that stop date imputation will not be applied to ongoing AEs. If the imputed stop date is greater than last the contact date, then the imputed stop date will be set to last contact date

9.0 Interim Analyses

A preliminary analysis of the study data will be performed and reported based on all patients' data up to the time when all patients from the Phase 1 part have completed at least six cycles of treatment or discontinued the study and the initial patients from the Phase 2 part have had at least one tumor assessment after six months of treatment or discontinued the study.

10.0 Statistical Methods

There will be no formal statistical testing in this study. Statistical analyses will be limited to descriptive summaries.

In general, continuous variables will be summarized by number of patients, mean, standard deviation (STD), median, minimum, and maximum. The mean and median will be presented to one more and the STD to 2 more decimal places than the precision of the variable, while the minimum and maximum will be presented at the same precision. Categorical variables will be summarized by frequency counts and percentages. Percentages will be presented to one decimal place. Where relevant, estimates will be presented with 95% two-sided confidence intervals (CI).

All tables, figures and listing will be presented separately for Phase 1 and Phase 2 portion of the study.

The Phase 1 summaries will be reported by dose levels within KY1044 single agent and KY1044 with atezolizumab combination groups.

The Phase 2 of the study will be reported by indication within KY1044 single agent and KY1044 in combination with atezolizumab, split by anti-PD-(L)1 naïve and pre-treated groups, and dose levels as appropriate.

Wherever possible, patients with the same tumor type who have received the recommended dose/schedule of KY1044 as single agent or in combination with atezolizumab will be pooled for analysis, respectively.

All analyses will be performed using SAS version 9.4 or higher.

10.1 Subject Disposition

The number and percentage of patients who completed the study, completed the 24 months survival followup, discontinued the study and a breakdown of the corresponding reasons for discontinuation.

The number and percentage of patients who discontinued the treatment prior to 48 months and a breakdown of the corresponding reasons for withdrawal from the treatment will be presented.

The subject disposition will be listed.

10.2 Demographic and Baseline Characteristics

The demographic characteristics will be summarized on the FAS and safety analysis set.

The demographic variables include age at screening (years), age groups in years ($\geq 18 - 64$, $\geq 65 - 84$ and ≥ 85), sex, ethnicity, race, weight (kg), height (m), body mass index (BMI) (kg/m²), and Eastern Cooperative Oncology Group (ECOG) status.

The following baseline characteristics will be summarized in the safety analysis set in both study phases:

- Medical history (coded by medical dictionary for regulatory activities [MedDRA] dictionary version 21.0 or higher and summarized by system organ class (SOC) and preferred term (PT))
- Tumor history
- Prior anti-cancer therapies
- Prior radiotherapies

Listings of the demographic characteristics, medical history, tumor history, prior anti-cancer therapy, prior cancer surgery, and prior radiotherapy will be presented.

10.3 Treatments

10.3.1 Extent of Study Drug Exposure

Exposure to study drug will be summarized for all patients in the safety analysis set. Descriptive statistics will be provided for study treatment duration (weeks), the total number of cycles started, number of infusions received, cumulative dose received (mg), absolute dose intensity (mg/week), and relative dose intensity.

The number and percentage of patients with at least 1 dose not administered, dose reduction or increase and at least 1 dose interruption will be presented along with a summary of the reasons for dose not administered, dose reductions and interruptions.

The bar plot of time to treatment will be presented for subject in FAS population.

A listing of study drug exposure will also be created. These data can be found on the Exposure KY1044- IV/Infusion Administration or the Exposure Atezolizumab- IV/Infusion Administration CRF pages.

10.3.2 Concomitant Medications

The medications received concomitantly with study drug, categorized by medication group and subgroup according to WHO Drug Enhanced [Version March 2016], will be summarized. The number and percentage of patients using each medication will be displayed together with the number and percentage of patients using at least one medication with each anatomical therapeutic chemical (ATC) and preferred term (PT).

Prior, concomitant and post study medications will be listed.

10.4 Important Protocol Deviations

Per PRA processes, important protocol deviations data will be entered into our clinical trials management system (CTMS). The study team and the Sponsor will conduct on-going reviews of the deviation data from CTMS and the resulting set of evaluable patients throughout the study, adjusting the deviation criteria as seems appropriate. The evaluable patients set must be finalized at the post-freeze data review meeting (or earlier), prior to database lock.

For each study phase, important protocol deviations for patients in the FAS will be reported by deviation category. Important protocol deviations will also be listed.

A separate listing of all COVID-19 related protocol deviations will be provided.

10.5 Efficacy Analyses

10.5.1 Hypothesis Testing Strategy and Multiplicity

No formal hypothesis testing and no measures will be employed to adjust the primary analysis and key secondary analysis for multiplicity are applicable for this study.

10.5.2 Primary Endpoint

Phase 1

- Safety: Incidence and severity of AEs and SAEs, including changes in laboratory parameters, vital signs and ECGs.
- Tolerability: Dose interruptions, reductions and dose intensity
- The incidence of DLTs with KY1044 as single agent during the first 21 days of treatment
- The incidence of DLTs with KY1044 in combination with atezolizumab during the first 21 days of treatment

Phase 2

• ORR per RECIST 1.1.

10.5.2.1 Imputation Methods

There will be no imputation of missing data values. Data on patients who withdraw early will be summarized up until the time of withdrawal.

10.5.2.2 Primary Analysis

The primary endpoints in Phase 1 are safety endpoints (see SAP Section 12.3 and 12.7).

The number and percentage of patients with confirmed CR or PR per RECIST 1.1 will be presented for all patients in FAS. The ORR will be accompanied by the 2-sided exact 95% Clopper-Pearson CI.

The waterfall plots of best percent change from baseline and maximum tumor size reduction from baseline as assessed by the investigator according to RECIST 1.1 will be provided for the FAS population.

The spider plot for percent change from baseline in tumor size will be provided for the FAS population.

Lesions assessed by the investigator (target, non-target, and new lesions) and investigator-reported overall tumor response assessment as per RECIST 1.1 will be presented in listings.

The subject-data listing will be provided for tumor assessment and tumor response.

10.5.2.3 Sensitivity Analyses

No sensitivity analyses is planned for the study.

10.5.2.4 Supplementary Analyses

No supplementary analyses is planned for the study.

10.5.3 Secondary Endpoints

Efficacy measures:

- BOR, PFS and DOR per RECIST 1.1
- ORR and PFS per immune-related iRECIST (Phase 1 and Phase 2)
- ORR per RECIST 1.1 (Phase 1 only)

• Survival rate at 12 and 24 months

Safety measures:

- Safety: Incidence and severity of AEs and SAEs, including changes in laboratory parameters, vital signs and ECGs (Phase 2).
- Tolerability: Dose interruptions, reductions and dose intensity (Phase 2).

PK measures:

• KY1044 PK measures (e.g., C_{max}, half-life); Serum concentration versus. time profiles.

Anti-drug antibodies:

• Presence and/or concentration of anti-KY1044 and anti-atezolizumab antibodies.

Biomarkers:

 Presence of tumor-infiltrating lymphocytes (TILs) as determined by expression of ICOS, FOXP3 and CD8 cells (IHC).

10.5.3.1 Best Overall Response

The counts and percentages of subject with BOR of CR, PR, SD and PD per RECIST 1.1 will be presented for Phase 1 and Phase 2 study phases for all patients in the FAS.

The overall response assessment by investigatory per RECIST 1.1 will be presented for Phase 1 and Phase 2 study phases for all patients in the FAS.

